5.3.2.2. RSV RNA \log_{10} viral load plaque assay (exploratory endpoints)

As exploratory analysis, the viral load measured using a quantitative viral culture (plaque assay) will be analyzed with descriptive statistics and mean (SE) graphs for both the actual values and changes from baseline. Additionally this analysis will be done by swab method (measured in the mid-turbinate nasal swabs and endotracheal samples from intubated subjects).

5.3.2.3. RSV clinical outcome

Length of hospital stay and time to readiness for discharge.

These time-to event variables will be analyzed as indicated above using Kaplan-Meier analysis, and will also be compared between each active treatment group and placebo using an accelerated failure time (AFT) model. .

Additionally, the time-to event data will be analyzed using the logrank test and Gehan-Wilcoxon method comparing each active treatment to placebo

Duration of intensive care unit (ICU) stay (hours) [Duration]

The duration in the ICU will be analyzed descriptively for all subjects and by subgroup of subjects staying / not staying in the ICU at the time of first dose of study drug.

Requirement for intensive care or supplemental support

The requirement for intensive care unit (ICU) stay, for oxygen supplementation, for noninvasive mechanical ventilation support, for invasive mechanical ventilation support, for supplemental feeding/hydration will be analyzed similarly. These requirement parameters will only be calculated for those subjects that don't require intensive care or supplemental support (depending on the parameter of interest) before first dose of study drug.

The proportion of subjects within the requirement categories (yes and no) will be shown in a frequency tabulation (with corresponding 95% CI) and per treatment group.

In addition, a stratified logistic regression model will be used to analyze the outcome

The analyses of the requirement parameters will answer the question:

Is there a treatment difference in preventing the use of intensive care or supplemental support?

Time to end of intensive care or supplemental support

These time-to event parameters will be analyzed for those subjects that require intensive care or supplemental support (depending on the parameter of interest) before first dose of study drug,

Kaplan-Meier analysis and stratified Gehan test to compare active treatment groups versus placebo will be used.

These time-to event parameters will answer the question:

Is there a treatment difference in the time to no longer requiring intensive care or supplemental support?

While we cannot integrate the results on the requirement for intensive care or supplemental support and the time to end of intensive care or supplemental support they are conceptually linked. We will combine the p-values for both independent tests for the comparison of each active group versus placebo using the method of Liptak^[3].

Additionally these time-to event parameters will be analyzed for all ITT-i subjects using Kaplan-Meier analysis as indicated above and using a stratified Gehan test to compare between treatment groups

Time to clinical stability and Time to return to pre-RSV disease level

These time-to event parameters will be analyzed as indicated above using Kaplan-Meier analysis.

The differences in time of active dose regimens versus placebo treatment will be estimated using a Cox proportional hazard model; as baseline covariates, stratification factors, absence/presence of other viral or bacterial infections, and baseline log₁₀ viral load will be added. Treatment effect versus placebo will be reported, including 95% confidence intervals. A Log-log plot of survival will be added to check the proportional hazard assumption.

Additionally, the time-to event data will be analyzed using the logrank test and Gehan-Wilcoxon method.

Incidence of acute otitis media and all-cause mortality

The incidence of acute otitis media and of all-cause mortality will be analyzed similarly. Note that these incidences are only analyzed if any subjects have acute otitis media or if any deaths occur.

The proportion of subjects with presence/absence of acute otitis media and who died yes/no will be shown in a frequency tabulation (with corresponding 95% CI) and per treatment group.

A stratified logistic regression model will be used to analyze the outcome.

Relationship between RSV RNA viral load and clinical outcome

The following relationships will be investigated:

RSV RNA log₁₀ viral load AUC_{0-144h} versus

- Requirement for oxygen supplementation
- Time to end of Oxygen supplementation

- Length of hospital stay
- Time to readiness for discharge
- Length of hospital stay since hospital admission
- Time to readiness for discharge since hospital admission
- Time to clinical stability
- Time to return to pre-RSV functional status

The definitions of these parameters can be found in sections [5.3.1](#).

A Tabulation of the requirement for oxygen supplementation will be presented by quartiles of viral load AUC_{0-144h} .

Kaplan-Meier analysis by quartiles of viral load AUC_{0-144h} will be done for the time to variables.

Relationship between RSV RNA viral load and signs and symptoms of RSV infection

The following relationships will be investigated:

Quartiles of viral load AUC_{0-144h} versus

- Severity of signs and symptoms of RSV infection as rated by the clinician.

The relationships described above will be explored by using the Spearman's rank correlation coefficients and scatterplots with smoother curve per treatment group.

The definitions of these parameters can be found in sections [5.3.2.1](#) and [5.4.1](#).

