Requirement for intensive care unit (ICU) stay	
Does the subject require admission to the ICU after first dose of study drug? Categories will be Yes (1) or No (0).
 
Only derive this parameter for subjects that were not in ICU before first dose of study drug.

Requirement for oxygen supplementation	
Does the subject require any oxygen supplementation (noninvasive or invasive) after first dose of study drug? Oxygen supplementation is indicated on the Oxygen Supplementation form: Type of supplemental oxygen administration.
 
Categories will be Yes (1) or No (0).
 
Only derive this parameter for subjects that didn't require oxygen supplementation before first dose of study drug.

Requirement for noninvasive nonmechanical ventilation	
Does the subject require noninvasive nonmechanical ventilation support after first dose of study drug? On the Oxygen Supplementation form, oxygen supplementation is

Measurement	Formula
support	
indicated but the type of supplemental oxygen administration doesn't equal "Non-Invasive Mechanical Ventilation" or "Invasive Mechanical Ventilation"?
 
Categories will be Yes (1) or No (0).
 
Only derive this parameter for subjects that didn't require oxygen supplementation before first dose of study drug.

Requirement for noninvasive mechanical ventilation support	
Does the subject require noninvasive mechanical ventilation support after first dose of study drug, as indicated on the Oxygen Supplementation form: Type of supplemental oxygen administration equals "Non-Invasive Mechanical Ventilation"?
 
Categories will be Yes (1) or No (0).
 
Only derive this parameter for subjects that didn't require noninvasive mechanical ventilation support or invasive mechanical ventilation support before first dose of study drug.

Requirement for invasive mechanical ventilation support	
Does the subject require invasive mechanical ventilation support after first dose of study drug, as indicated on the Oxygen Supplementation form: Type of supplemental oxygen administration equals "Invasive Mechanical Ventilation"?
 
Categories will be Yes (1) or No (0).
 
Only derive this parameter for subjects that didn't require invasive mechanical ventilation support before first dose of study drug.

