Requirement for supplemental feeding/hydration	
Does the subject require supplemental feeding/hydration (e.g. IV catheter/nasogastric tube) after first dose of study drug?
 
Categories will be Yes (1) or No (0).
 
Only derive this parameter for subjects that didn't require supplemental feeding/hydration before first dose of study drug.

Time to end of intensive care	The time from first study drug intake until the time of

Measurement	Formula
unit (ICU) stay (hours) [Time-to event]	
discharge from the ICU after which the subject was not readmitted to the ICU (= event)
 
Subjects who complete or withdraw from the study prior to the event will be censored at the date of completion or withdrawal. If the time is not available they will be censored at 12:00. In case of death the subject will be censored at the maximum observed number of hours until the occurrence of the event or censoring for all subjects achieving the event or being censored because of study completion or withdrawal. If no admittance to the ICU was necessary, the value will be set to 0.
 
(Date and time of event or censoring - date and time of first dose of study drug)/3600, rounded to one decimal

Time to end of Oxygen supplementation (hours) [Time-to event]	
The time from first dose of study drug start of oxygen supplementation to the last end date and time of any oxygen supplementation (= event) in hours (Oxygen supplementation is indicated on the Oxygen Supplementation form: Type of supplemental oxygen administration.). (Note: it is not necessary that the subject started on oxygen at baseline.)
 
If the end date is missing, the end date is considered to be after study completion or withdrawal.
 
Subjects who complete or withdraw from the study prior to the event will be censored at the date of completion or withdrawal. If the time is not available they will be censored at 12:00. In case of death the subject will be censored at the maximum observed number of hours until the occurrence of the event or censoring for all subjects achieving the event or being censored because of study completion or withdrawal.
 
If no oxygen supplementation was necessary after first dose of study drug, the value will be set to 0 hours.
 
(Date and time of event or censoring - date and time of first dose of study drug)/3600, rounded to one decimal

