Time to end of noninvasive mechanical ventilation support (hours) [Time-to event]	
The time from first dose of study drug to the last end date and time of noninvasive mechanical ventilation and invasive mechanical ventilation support (= event) in hours. Noninvasive mechanical ventilation and invasive mechanical

Measurement	Formula
	
ventilation are defined as indicated on the Oxygen Supplementation form: Type of supplemental oxygen administration.
 
Derivation similar as “Time to end of Oxygen supplementation”

Time to end of invasive mechanical ventilation support (hours) [Time-to event]
	
The time from first dose of study drug to the last end date and time of invasive mechanical ventilation support (= event) in hours. Invasive mechanical ventilation support is defined as indicated on the Oxygen Supplementation form: Type of supplemental oxygen administration.
 
Derivation similar as “Time to end of Oxygen supplementation”

Time to end of supplemental feeding/hydration (hours) [Time-to event]
	
The time from first dose of study drug to the last end date and time of supplemental feeding/hydration (e.g. IV catheter/nasogastric tube) (= event) in hours.
 
Derivation similar as “Time to end of Oxygen supplementation”

Time to return to pre-RSV disease level for respiratory rate (hours) [Time-to event]
	
The time from first dose of study drug until the time to return to pre-RSV disease level. The return to pre-RSV disease level occurs when the observed value of the parameter is indicated by the investigator as normal, and no later observed values are indicated by the investigator as abnormal (=event).
 
Normalization of respiratory rate (RR) will be derived from the answer to the corresponding question in the questionnaire “is this Respiratory Rate value normal for this patient?”
 
If no deterioration from pre-RSV disease levels occurred, the time will be set to time of first dose of study drug and the value will be set to 0 hours.
 
Subjects with an abnormal value at the last assessment will be censored at that time. Subjects for which this last assessment is the baseline assessment will be censored at time 0.

Measurement	Formula
	(Date and time of event or censoring - date and time of first dose of study drug)/3600, rounded to one decimal

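### The support analyses select children by support before first dose, without saying it must be ongoing at dosing, so children already weaned can enter time-to-end at 0 hours and drop out of the prevention analysis

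*SAP*

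**What the plan says.** SAP 5.3.2.3 asks two linked questions about intensive care and supplemental support.

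- **Time to end.** The analysis is done "for those subjects that require intensive care or supplemental support (depending on the parameter of interest) before first dose of study drug", with Kaplan-Meier estimates and a stratified Gehan test of each active group against placebo.
- **Requirement (prevention).** The analysis is done in the complement. SAP 5.3.1.3 repeats the restriction parameter by parameter. The oxygen variable is derived only for children who did not "require oxygen supplementation before first dose of study drug". For intensive care the rule is: "Only derive this parameter for subjects that were not in ICU before first dose of study drug".

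The p-values from the two analyses are then combined by the Liptak method. Time-to-end is also analysed in all ITT-i subjects.

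The value rule for oxygen in SAP 5.3.1.3 is: "If no oxygen supplementation was necessary after first dose of study drug, the value will be set to 0 hours". Ventilation and supplemental feeding/hydration inherit it through the words "Derivation similar as". The ICU rule is narrower: "If no admittance to the ICU was necessary, the value will be set to 0".

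One analysis in the same section uses a different time reference. ICU duration is summarised by subgroups of "subjects staying / not staying in the ICU at the time of first dose of study drug".

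**The concern.** Before first dose and at first dose are different conditions. A child given oxygen on admission and weaned before dosing meets the first and not the second. As written, that child is taken out of the question whether new use is prevented, although still at risk of it. The child is placed instead in the question of how soon support ends, with an answer fixed before any study drug was given.

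Values at 0 hours carry no information about treatment, and the Gehan test gives the earliest times the most weight. Such children therefore dilute the comparison, and the diluted p-value goes into the Liptak combination. They also pull the Kaplan-Meier median below that of the children who were on support when treatment began.

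**Working it through.** **1. Applying the rules to a child with support before dosing**

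| Child | Time-to-end set | Value | Requirement set |
|---|---|---|---|
| Support ongoing at first dose | in | positive | out |
| Weaned before dose, none later (oxygen, ventilation, feeding/hydration) | in | 0 h | out |
| Weaned before dose, restarted later | in | positive | out, so the restart is not counted as new use |
| Discharged from ICU before dose, not readmitted | in | not clearly defined | out |

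The 0 is an assigned value; the censoring rules are stated separately. In the ICU row the child was admitted, so the zero rule for no admittance does not clearly apply. The formula (last ICU discharge minus first dose) would give a negative time.

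**2. Size of the dilution**

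The documents give no power figure for these analyses, so there is none to reproduce. The stated 97% concerns the primary endpoint and is not an input here.

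Let f be the share of the time-to-end set that sits at 0 h, equal in both arms. Without censoring, the Gehan test is the Wilcoxon test.

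- The difference of the Wilcoxon probability from 0.5 shrinks by (1−f)².
- The tie-corrected variance factor is 1−f³.
- Restricting to children on support at dosing leaves a fraction (1−f) of the sample.

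The noncentrality as written, relative to the restricted set, is therefore R = (1−f)^1.5 / √(1−f³), and the required sample size rises by 1/R². The pooled median reads the (0.5−f)/(1−f) quantile of the children truly on support.

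| f (assumed) | R | 1/R² | Quantile read by the median |
|---|---|---|---|
| 5% | 0.926 | 1.17 | 47th |
| 10% | 0.854 | 1.37 | 44th |
| 20% | 0.718 | 1.94 | 37.5th |

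**3. Power by simulation**

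Inputs, all assumed and none from the documents: 35 children per arm on support at dosing, lognormal times with time ratio 0.58 and log-SD 0.8, no censoring, two-sided Wilcoxon test at 5%, weaned children divided between arms at random.

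| f | Power | Analysed per arm, 35/(1−f) |
|---|---|---|
| 0% | about 79% | 35.0 |
| 2% | about 76% | 35.7 |
| 5% | about 70% | 36.8 |
| 10% | about 63% | 38.9 |

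SAP 5.1.1 expects an ITT-i set of 120, which is 120/3 = 40 per arm. At f = 20% this set-up would need 35/0.8 = 43.8 per arm and at 30% it would need 35/0.7 = 50. Those rows are not used. The 10% row already needs 38.9/40 = 97% of an arm to have had support before dosing.

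A second illustration fixes the set at 40 per arm with pre-dose support, exponential times and hazard ratio 2 (again assumed). Power as written against an at-dose split is 55% against 70% at f = 10%, and 38% against 65% at f = 20%.

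**4. Type 1 error**

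With no treatment effect, the second set-up rejects in 4% to 5% of runs under either split. This is as expected, because the split uses only pre-dose data in a randomised, blinded trial.

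**The case against.** **The wording may mean status going into dosing.** The SAP verb is in the present tense, baseline is defined as the last record before first intake, supplemental oxygen at baseline is a listed characteristic and covariate, and time to no longer requiring support presupposes that it is required. This stands in part. A reader might infer that the SAP deliberately splits on any prior use. It does not say so; that is the plain reading of an undefined phrase. But the past-tense derivations in 5.3.1.3 lean toward the plain reading, no look-back limit is given, and the ICU-duration text shows that the authors use different words for status at dosing.

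**The 0-hour rule serves another analysis.** Never-users need a value when time-to-end is run in all ITT-i subjects. That is true, and that analysis does not depend on the split. It does not repair the restricted Gehan test, the requirement set or the Liptak input.

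**Few children may be affected.** Screening is to follow admission as soon as possible, and dosing must begin within 4 hours of randomisation. This limits pre-dose weaning. It does not exclude it: randomisation may be up to 5 days after symptom onset, and protocol section 8 allows oxygen to be withdrawn as appropriate.

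**First-ever need is a legitimate question.** It is. But then restarts after weaning are counted nowhere as new use, and the weaned children still sit in the time-to-end set.

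**Conclusion.** The concern holds as a gap in definition. Followed as written, SAP 5.3.1.3 and 5.3.2.3 put a child weaned before dosing into time-to-end at 0 hours if no further oxygen, ventilation or supplemental feeding/hydration is needed, and exclude that child from the prevention analysis. For ICU the value is simply unclear.

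Two stronger readings are tempting and not supported. One is that every weaned child becomes a 0-hour event: those who restart get a positive time, and the 0-hour rule is not established for ICU discharge before dosing. The other is that the comparison is biased or falsely positive: type 1 error is not inflated, and the primary endpoint is untouched.

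The consequence is lost power and a misdescribed median in secondary analyses. Its size depends on the share weaned, which is unknown: nothing is lost at 0%, about 9 points of power at 5% (79% to 70%) and about 16 at 10% (79% to 63%), under inputs that are all assumed. Counts for ventilation or ICU could be much smaller than the 35 per arm used here.

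**What to change.** In SAP 5.3.1.3 and 5.3.2.3, for oxygen, ventilation, ICU and feeding/hydration:

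- Define the time-to-end set as children with the support ongoing at the time of first dose.
- Define the requirement set as children with the support not ongoing at the time of first dose, and count a restart after weaning as new use.
- Keep the 0-hour rule for analyses that cover all ITT-i subjects, including time to clinical stability, which reuses the oxygen and feeding derivations. State there the value for a child discharged from ICU before dosing.
- If first-ever need is also of interest, report it as a subgroup of the requirement analysis.

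The two sets stay disjoint, so the basis for the Liptak combination is unchanged. The cost is a few words, to be settled before unblinding. The derivations already use start and end dates and times, so no new data are needed and trial conduct does not change.
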